The tomographic or radiographic findings will be interpreted using the scoring system previously described by Cai et al (46). After the analysis by the assigned radiologist of the hospital center, the data generated by CT or X-ray will be submitted to two independent radiologist physicians, both blinded to the corresponding group of participants and the corresponding clinic. These specialists will assign a Pulmonary Score 1 (SP1) according to the findings they observe, based on three categories:

- 1 = Normal attenuation
- 2 = Ground-glass opacity
- 3 = Consolidation

Each lung will be divided into 3 zones with limits defined as follows:

Upper zone: area above the level of the carina.

Middle zone: area between the level of the carina and the inferior pulmonary vein.

Inferior zone: area below the level of the inferior pulmonary vein.

In this way, a total of 6 pulmonary areas will be delimited, each of which will receive a score according to the following scale of distribution of compromised lung parenchyma or Pulmonary Score 2 (SP2):

- 0 = Normal
- 1 = 1% to 25% involvement
- 2 = 25% to 50% involvement
- 3 = 50% to 75% involvement
- 4 = More than 75% involvement

The scores of each lung area will be summed to obtain the Total Affectation (AT) grade. Finally, AT will be multiplied by SP1 to obtain the Total Cumulative Scale (ETA), which comprises a range from 0 to 72. A change of "Improvement" on CT or chest X-ray will be defined as an ETA lower than the previous value obtained at the start of treatment or from the previous imaging studies. A "worsening" change will be defined as an ETA greater than the previous value obtained at the start of treatment or previous imaging studies. The stability of the picture will be defined as "Constant" when the ETA is equal to the previous value obtained at the beginning of treatment or from previous imaging studies.

Statistical Analysis Plan

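### In the complementary imaging analysis any difference in ETA counts as change, with shared band limits, no rule for combining two readers and no stated masking of image order, so reading variation alone can move a stable patient out of Constant

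*Combined protocol and SAP*

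**What the plan says.** The imaging rules are in section 4.1 of Version B, under computerized axial tomography and chest radiography. Version A has the same text.

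- **Score.** Each lung has three zones, so "a total of 6 pulmonary areas will be delimited". Each zone gets an involvement score (SP2) from 0 to 4, and the six scores are summed to AT. An attenuation score (SP1) runs from 1 to 3. "Finally, AT will be multiplied by SP1 to obtain the Total Cumulative Scale (ETA), which comprises a range from 0 to 72".
- **Bands.** SP2 score 1 ends at 25%, and the next line reads "2 = 25% to 50% involvement". Score 3 begins at 50%. Score 4 starts above 75%, so that limit is not shared.
- **Labels.** *Improvement* "will be defined as an ETA lower than the previous value obtained at the start of treatment" or from an earlier image. *Worsening* "will be defined as an ETA greater than the previous value obtained at the start of treatment or previous imaging studies". *Constant* applies "when the ETA is equal to the previous value obtained at the beginning of treatment or from previous imaging studies". No minimum change is given.
- **Readers.** After the hospital radiologist, two further radiologists score separately, "both blinded to the corresponding group of participants and the corresponding clinic". No average, consensus, adjudication or agreement statistic is described.
- **Image handling.** Section 5 has the DICOM files anonymised before they go to the radiologists. Neither section mentions study dates or reading order.
- **Status.** Imaging is listed among the complementary analyses, outside the primary and secondary outcomes. The Statistical Analysis Plan names no imaging analysis.

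**The concern.** A three-way label with zero tolerance treats every difference between two visual readings as a change in the patient. ETA combines six graded zones and a multiplier, so a disagreement in any one of them can move a patient out of *Constant*. Three gaps add to this:

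- A zone at exactly 25% or 50% has two permitted scores.
- If one reader's ETA falls and the other's rises, the plan gives no answer, and in an open-label study the choice could be made after the data are seen.
- The comparison is before against after, and the control group comes from past records. If dates were visible, they could tell a reader which image came later. If control images come from a different period, dates could also tell which group the patient belongs to.

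What is at stake is the meaning of a reported proportion improved on imaging. Without an allowance for reading error, that proportion mixes real change with measurement variation in unknown shares.

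**Working it through.** **Range of the scale.** The maximum is 6 zones × SP2 of 4 × SP1 of 3 = 72 and the minimum is 0. The plan's 0 to 72 reproduces.

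**Smallest usual step.** With SP1 fixed, one band in one zone moves AT by 1 and ETA by SP1, that is 2 points for ground-glass and 3 for consolidation.

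**Inputs for the noise check.** Six zones and the label rule come from the plan. The per-zone misread rate q does not, so it is an assumption and a range is shown. For a patient whose lungs have not changed:

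- each zone on each occasion is read one band too high with probability q/2 and one band too low with probability q/2
- SP1 is read without error
- errors are independent
- the 0 and 4 limits are ignored at first

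**Formula.** The difference in AT between two occasions is then the sum of 12 independent errors (6 zones × 2 occasions). The label is *Constant* only if that sum is 0:

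P(Constant) = Σ over j of [12! / (j! j! (12−2j)!)] × (q/2)^(2j) × (1−q)^(12−2j)

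At q = 10%, the terms for j = 0, 1, 2 and 3 are 0.2824 + 0.1151 + 0.0080 + 0.0002 = 0.406 after rounding. So P(changed) = 0.594, and by symmetry P(*Improvement*) = 0.297.

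| Assumed q | Constant | Labelled changed | Of which Improvement | False Improvement if all 20 treated patients were stable |
|---|---|---|---|---|
| 2% | 79.6% | 20.4% | 10.2% | 2.0 |
| 5% | 59.1% | 40.9% | 20.5% | 4.1 |
| 10% | 40.6% | 59.4% | 29.7% | 5.9 |
| 20% | 26.5% | 73.5% | 36.7% | 7.3 |

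The same number would be labelled *worsening*.

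**Sensitivity.** A simulation with zone scores kept within 0 to 4 and SP1 misread in 0% to 10% of reads gave 35% to 47% labelled changed at q = 5%, 53% to 62% at 10% and 69% to 75% at 20%.

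**Shared limits.** The extreme case is all six zones at exactly 25%: AT may be 6 or 12, so ETA may be 12 or 24 at SP1 = 2, or 18 or 36 at SP1 = 3. This bounds the ambiguity and is not a typical size.

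**Would it help to require both readers to agree?** At q = 10% with independent reader errors, false *Improvement* falls from 0.297 to 0.297² = 0.088. But a real one-band improvement in one zone is detected by one reader with probability 0.297 + 0.406 = 0.703, and by both with probability 0.703² = 0.494. False change is exchanged for missed change.

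**What averaging does.** Each reading error has variance q, so one reader's ETA change has reading-error SD = SP1 × √(12q). At q = 10% that is 2 × 1.095 = 2.19 points or 3 × 1.095 = 3.29 points. Averaging two readers with independent errors divides this by √2, giving 1.55 or 2.32. The error has mean zero, so a mean change is not shifted by it. In 20 patients at SP1 = 3 it adds a standard error of 2.32/√20 = 0.52 points.

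**The case against.** The strongest case on the other side is that this is a complementary analysis with no named test, the misread rate is assumed, and symmetric error favours neither treatment nor control. The patients are acutely ill inpatients followed for up to 20 days. Many will truly change, and the calculation for stable patients does not say what share of the reported labels is noise. The Statistical Analysis Plan already summarises quantitative data by mean and SD or by median, which would cover ETA values, though it does not mention ETA change. All of this stands, and it makes the point minor. None of it supplies a tolerance, a rule for two readers or a single band for 25% and 50%.

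A reader might infer more than the documents support:

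- **That image order is open to the readers.** The plan is silent. It states blinding to group and anonymisation of files, and says neither that dates are kept nor that they are removed.
- **That results lean towards *Improvement*.** This would need readers to know which image is later and to score accordingly. Neither is stated, and nothing here estimates such a lean.
- **That the rule misclassifies even with perfect reading.** In the calculation every false label comes from misreading; at q = 0 there are none. The only ambiguity in the rule itself is at exactly 25% or 50%.
- **That one-point differences drive the problem.** They fall under the rule but are rare in abnormal lung: they made up under 0.2% of simulated pairs.

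**Conclusion.** The point holds as a minor defect of definition. The label has no tolerance for reading error, two band limits are shared, the two readers' scores are not combined, and no masking of image date or order is stated. Under an assumed symmetric one-band misread rate of 2% to 20% per zone, with SP1 read without error, 20.4% to 73.5% of truly unchanged patients would be labelled changed, half in each direction. The percentages depend on that assumption, but the direction of the finding does not: even at 2%, about one stable patient in five leaves *Constant*. The shared limits add little beyond ordinary misreading near a cut-off. The documents support no conclusion that the imaging result is biased in favour of treatment, and the primary and secondary outcomes are untouched.

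**What to change.** 1. **Main summary.** Average the two existing readers' ETAs at each time point. Make the change from the start-of-treatment image, analysed as a continuous result, the main imaging summary. Keep the three-way label as description only. If control images are included, state which image serves as their reference.
2. **Bands.** Give each shared limit to one band, for example 1% up to 25%, over 25% to 50%, over 50% to 75%, and over 75%. Because the plan takes its scoring from a cited source, record whether this departs from it.
3. **Image handling.** In the anonymisation step already planned in section 5, remove study dates and send each patient's images in random order. This also protects the stated blinding to group, given retrospective controls.

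Do not require both readers to agree before a label is given. At a 10% misread rate with independent errors, that would cut detection of a real one-band improvement from 70% to 49%.

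No extra reader, image or patient is needed. The cost is a few lines of protocol text, a little more preparation of the files and less weight on an easily quoted proportion improved. If the readers share errors, averaging will gain less than the √2 shown.

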Scientific evidence proves the absence of short or long-term adverse effects of thymomodulin, obtaining significant results in the treatment of patients with immunological vulnerability in various respiratory pathologies (23). Taking this into account, it can be considered a promising alternative to combat the COVID-19 pandemic. The following sections will discuss the methodology of the clinical trial that will be used to evaluate its efficacy as a therapeutic option.

Hypothesis

Oral administration of thymic peptides (Unicahsina) is a safe and effective therapy for the management of patients with COVID-19 respiratory onsets.

General Objective

To demonstrate the therapeutic efficacy and safety of thymic peptides (Unicahsina) in patients with COVID-19 respiratory disease.

Specific objectives

- 1. To evaluate the safety of thymic peptides (Unicahsina) by monitoring adverse events using the Common Terminology Criteria for Adverse Events Version 5.0 (CTCAE v5.0) and side effects using the General Assessment of Side Effects (GASE).
- 2. Determine the time to participant recovery, according to a clinical ordinal progression scale.
- 3. To perform survival analysis in patients diagnosed with COVID-19 and treated with thymic peptides (Unicahsina).

SECTION 2 - DESCRIPTION OF THE POPULATION

2.1 Number of participants: 20 participants.

2.2 Describe the population:

Patients with diagnosis of COVID-19 confirmed by RT-qPCR testing, viral antigen detection or antibody detection plus associated symptomatology. The study will be performed in patients over 20 years of age without distinction of sex, race, religion, or socioeconomic status. Since the population under 20 years of age presents mostly mild or asymptomatic symptoms, with a mortality rate between 0% and 0.2%, it was decided to exclude this age range.

This research will involve elderly patients and those with comorbidities. The current COVID-19 pandemic has shown that this group of patients has the highest mortality rate, exposing the need to discover safe and effective therapies. Therefore, and given the innocuous profile that thymic peptides possess, we consider their use in this population.

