Should any of the participants decide to withdraw from the study voluntarily or request self-discharge, another patient will be added to the study until 20 patients have reached conclusion either by medical discharge or death within a 20-day hospitalization follow-up. Patient data will be used up to the date of voluntary withdrawal or self-discharge.

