Measured in days to clinical recovery that will be defined as the first day, during the 20 days after enrollment, on which a patient met the criteria for category 1, 2, or 3 on the eight-category ordinal scale. The categories are as follows: 1, not hospitalized and no limitations of activities; 2, not hospitalized, with limitation of activities, home oxygen requirement, or both; 3, hospitalized, not requiring supplemental oxygen and no longer requiring ongoing medical care; 4, hospitalized, not requiring supplemental oxygen but requiring ongoing medical care (related to Covid-19 or to other medical conditions); 5, hospitalized, requiring any supplemental oxygen; 6, hospitalized, requiring noninvasive ventilation or use of high-flow oxygen devices; 7, hospitalized, receiving invasive mechanical ventilation or extracorporeal membrane oxygenation (ECMO); and 8, death.

2) Number of participants with treatment related adverse events as assessed by the Common Terminology Criteria for Adverse Events Version 5.0 (CTCAE v5.0) [Time Frame: Up to 20 days]

Number of participants who experience adverse events \geq Grade 3, as defined by the CTCAE v5.0.

3) Number of participants with treatment related side effects as assessed by the General Assessment of Side Effects (GASE) [Time Frame: Up to 20 days]

Number of participants who experience severe side effects as defined by the GASE.

Secondary Outcomes measures

1) Overall survival defined as the time from the start of treatment until death due to any reason [Time Frame: Up to 20 days]

Time for overall survival will be measured in days.

Other complementary analyzes

Computerized axial tomography and chest radiography

A Computerized tomography without contrast will be performed, with the patient in the supine position and the image acquisition will be carried out at the end of inspiration. The following parameters will be requested to obtain axial images: 1.25 mm thick, 1.25 mm interval, 120 kVp. If it is possible, chest radiographs will be requested in posteroanterior projection. However, in patients whose clinical condition warrants it, anteroposterior radiography will be considered. The images will be obtained at the moment of maximum inspiration, either with instruction to the patient or by controlling the ventilator console in the case of intubated patients.

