All quantitative data will be described using parameters such as the mean \pm standard deviation, or as the median (minimum and maximum). Qualitative data will be described by the number of cases (proportion%). Patient characteristics will be compared using the chi-square test or Fisher's exact test for categorical data. For continuous variable data, the Wilcoxon test or Student's t test will be employed. The analysis of time to a particular event will be carried out using the Kaplan-Meier method, and the analysis of differences between groups will be calculated with the log-rank test. The Cox proportional-hazard model will be used to estimate the hazard ratio and 95% confidence interval (CI). Propensity score matching methodology will be used to generate the comparison group from the clinical records. A p-value less than 0.05 will be required to establish significance. All analyses will be performed using SPSS and GraphPad Prism software.

SECTION 5 - ANONYMITY AND CONFIDENTIALITY OF DATA

The data will be obtained from the healthcare center assigned to treat positive cases of COVID-19, through the clinical record designed as an instrument for this study. The laboratory and imaging test reports, as well as the clinical records, will be digitized and sent to the principal investigators using the SOPHOS encryption software. This last part will ensure the confidentiality of each patient's data between devices while transferred. Access will be given to the Dirección General de Vigilancia del Marco Normativo de la Secretaría de Salud de Honduras (General Directorate for Regulatory Framework Surveillance of the Ministry of Health of Honduras) for the monitoring of the study. The hospital will have a password-protected electronic device. The access will be limited exclusively to medical doctors assigned for the study.

The physical documents will be attached to the patient clinical file at the end of the hospitalization.

For the data produced by CT or chest x-ray, the HOROS software will be used to visualize and anonymized DICOM files before sending them to radiologists. The confidentiality in transferring this information will be ensured by using the SOPHOS software.

SECTION 6 - POTENTIAL RISKS AND BENEFITS

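### The two primary safety counts have no planned confidence interval or criterion, although the objective is to demonstrate safety in about 20 patients

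*Combined protocol and SAP*

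**What the plan says.** Version B, General Objective: "To demonstrate the therapeutic efficacy and safety of thymic peptides". The hypothesis just above it likewise presents the therapy as safe. Section 2.1 sets the size: "2.1 Number of participants: 20 participants". Section 2.2 replaces participants who withdraw or discharge themselves, so that "another patient will be added to the study until 20 patients have reached conclusion either by medical discharge or death", and keeps their data up to the date they leave.

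Under Primary outcome measures in section 4.1, outcomes 2 and 3 are the safety outcomes:

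- Outcome 2 is titled "Number of participants with treatment related adverse events as assessed by the Common Terminology Criteria for Adverse Events Version 5.0 (CTCAE v5.0", but the definition beneath it counts participants with Grade 3 or higher adverse events and does not repeat the restriction to treatment-related ones.
- Outcome 3 is defined as "Number of participants who experience severe side effects as defined by the GASE". Its title also carries the treatment-related restriction, which the definition leaves out.

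Both have a time frame of up to 20 days. The paragraph on administration in section 4.1 says that information is collected only until discharge or ICU referral.

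The Statistical Analysis Plan names neither safety outcome. Three of its sentences bear on them:

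- on describing categorical data: "Qualitative data will be described by the number of cases (proportion", followed by a percent sign;
- on testing: "Patient characteristics will be compared using the chi-square test or Fisher's exact test for categorical data";
- on intervals: "The Cox proportional-hazard model will be used to estimate the hazard ratio and 95% confidence interval (CI".

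It sets a significance level of 0.05 without saying whether one- or two-sided. It gives no acceptable event rate, threshold or decision rule for safety. The Version A plan has the same wording.

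**The concern.** A single-arm safety count in about 20 people carries little information about events of moderate frequency, and a percentage alone does not show this. The plan gives a measure of precision for the hazard ratio but none for two outcomes listed at the same primary level. The tests it names are assigned to patient characteristics. The 0.05 rule cannot be applied to a single-arm count without a reference rate. An objective phrased as demonstrating safety is therefore linked to a number that has neither an interval nor a criterion.

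What is at stake is the conclusion the trial may draw. A result of 0 (0%) could be taken as meeting the objective while still being compatible with a severe-event rate that most readers would not call safe. The point does not depend on enrolling more patients. It concerns what may be said from the number already planned.

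**Working it through.** **Inputs.** n = 20 (section 2.1), stated without derivation, so the plan has no precision or power figure to reproduce. Two binary safety outcomes (section 4.1). Confidence level 95%, taken from the plan's interval for the hazard ratio. Two-sided is an assumption, because the plan does not state sidedness.

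**Step 1: upper limit when no events are seen.** The exact (Clopper-Pearson) two-sided 95% limit for 0 of n is 1 − 0.025^(1/n). With n = 20: 1 − 0.025^(1/20) = 1 − 0.8316 = 0.1684, so the interval is 0 to 16.8%.

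**Step 2: sensitivity to the method, for 0 of 20.**

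| Method | Formula | Upper limit |
|---|---|---|
| Exact, two-sided 95% | 1 − 0.025^(1/20) | 16.8% |
| Wilson, two-sided 95% | z²/(20 + z²), z = 1.96 | 16.1% |
| Rule of three | 3/20 | 15.0% |
| Exact, one-sided 95% | 1 − 0.05^(1/20) | 13.9% |

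None of these is below 13.9%.

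**Step 3: small non-zero counts.** Exact two-sided 95% intervals from beta quantiles, with lower limit Beta(0.025; x, 20 − x + 1) and upper limit Beta(0.975; x + 1, 20 − x):

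| Count | Estimate | 95% interval |
|---|---|---|
| 1/20 | 5% | 0.1% to 24.9% |
| 2/20 | 10% | 1.2% to 31.7% |
| 3/20 | 15% | 3.2% to 37.9% |

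**Step 4: how often a zero count arises when the true rate is not zero.** P(0 of 20) = (1 − p)^20.

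- p = 5%: 0.95^20 = 0.358
- p = 10%: 0.90^20 = 0.122

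**Step 5: the denominator.** Withdrawals are replaced and their data kept, so the number treated may exceed 20. The documents do not give the likely number; 22 and 25 are assumed for illustration. With zero events, the two-sided exact limit is 1 − 0.025^(1/22) = 15.4% or 1 − 0.025^(1/25) = 13.7%. The conclusion does not change.

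**Step 6: what the interval does not cover.** The binomial limit treats every participant as observed for the same period. Because data collection ends at discharge or ICU referral, a low count may partly reflect short observation. The limit then describes events seen while under observation and does not bound the 20-day risk.

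**The case against.** A reader might infer that the trial will present 0 of 20 as proof of safety. The documents do not support this. No section says how any safety count will be interpreted. The word *demonstrate* sits in the general objective, while the first specific objective speaks only of evaluating safety by monitoring events. Section 6.1 also concedes that unknown adverse effects in COVID-19 patients remain possible. What stands is that a bare zero *could* be read that way, and that the plan offers nothing to limit the reading.

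A reader might also infer that the plan restricts safety reporting to counts and percentages. It does not. The sentence on categorical data is generic and does not rule out an interval. The gap is that none is pre-specified, which leaves the choice until the data are known.

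Nor should the result be put as an inability to exclude a rate of one in six. That holds only narrowly and only under the two-sided convention (16.84% against 16.67%). At a true rate of one in six, zero events would occur with probability (5/6)^20, about 2.6%, and the one-sided 95% limit of 13.9% does exclude it. Any such statement needs its confidence level and sidedness.

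Finally, with a count and a denominator in the report, anyone can compute the interval, and there is no formal safety decision for its absence to distort. That is fair, and it keeps the point moderate. It does not remove it: these are primary outcomes, the denominator is itself undefined, and the objective is worded as something to be shown.

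**Conclusion.** The point holds as an omission with a practical consequence. For two of three primary outcomes, a number and percentage is the only analysis the plan assigns, with no measure of precision and no criterion against which safety could be demonstrated. With zero events in 20, the data would be compatible with a severe-event rate of up to 16.8% (two-sided exact 95%), or 13.9% under a one-sided 95% limit. A true 10% rate would go unseen in about one trial in eight (12%).

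These figures assume exactly 20 participants, independent outcomes and complete observation over the period described. They do not depend on which reading of outcome 2 applies, but the count does: all Grade 3 or higher events in hospitalised patients may be far more numerous than those judged treatment-related. The plan should change, but the gap does not invalidate any estimate already specified.

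**What to change.** - Add to the Statistical Analysis Plan: each primary safety count is reported with its percentage and a two-sided exact (Clopper-Pearson) 95% confidence interval.
- State the denominator as all participants who received at least one dose, including those who withdrew and were replaced.
- Reword the safety part of the general objective from demonstrating safety to estimating the incidence of severe events.
- Tie the conclusion to the upper limit, its confidence level and the observation period. For example: *with no events among 20 treated participants, the two-sided exact 95% upper limit for the proportion with a severe event while under observation, up to discharge or ICU referral, is 16.8%.* Report the length of observation alongside it, and do not present the limit as a bound on the 20-day risk.
- In section 4.1, reconcile the titles and definitions of outcomes 2 and 3, stating whether all qualifying events count or only those judged treatment-related.

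This takes a few sentences and no extra patients, data or procedures. The downside is a more modest safety claim.

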4.1 Study design

This is a single-arm, open-label, phase II clinical trial to evaluate the safety and efficacy of thymic peptides in the treatment of hospitalized COVID-19 patients in Honduras, at the Hospital de Santa Bárbara Integrado. A participant-level comparison will be made based on registry data of the Hospital de Santa Bárbara Integrado, after propensity score matching.

In total, 20 patients will be recruited from the designated hospital for COVID-19 patient care, including those who have signed informed consent and who meet the inclusion criteria. For the generation of the comparison group through data from clinical records, it will be carried out by authorization from the Hospital de Santa Bárbara Integrado, given its retrospective nature, without experimental intervention.

Clinical characterization

Once the protocol is started, the information corresponding to the general data, signs, symptoms, physical examination and laboratory values of each patient will be recorded daily in the data collection instrument. The record will be made on paper, which will be digitized and sent under encryption to the principal investigators every day.

As a quantitative method, the following laboratory findings will be considered to evaluate clinical progress, according to the requirement and availability of the hospital:

- Complete blood count
- C-reactive protein
- D-dimer
- Ferritin
- Procalcitonin
- Lactate
- AST

- ALT
- BUN
- Creatinine

Administration of thymic peptides (Unicahsina)

Thymic peptides (Unicahsina) will be administered in an oral dose of 250 mg per day. In the intubated patient, the administration will be done through a nasogastric tube. The presentation of thymic peptides (Unicahsina) will be in lyophilized form, which will be diluted in 50 ml of drinking water prior to administration. It should be administered on an empty stomach one hour before or two hours after a meal. If the patient is discharged, or if they need to be referred to an ICU, all the information will be gathered up to that moment and the administration of Unicahsina will be stopped.

Primary outcome measures

1) Time to participant recovery [Time Frame: During hospitalization for up to 20 days.]

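### The plan compares participants with their propensity-matched registry controls by significance tests and attaches no balance measure to the match; with about 20 per group such tests miss imbalances large enough to bias the hazard ratio

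*Combined protocol and SAP*

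**What the plan says.** Version B, 4.1 Study design, states: "In total, 20 patients will be recruited from the designated hospital for COVID-19 patient care". It adds: "A participant-level comparison will be made based on registry data of the Hospital de Santa Bárbara Integrado, after propensity score matching". The Statistical Analysis Plan under Section 4 gives the matching one sentence: "Propensity score matching methodology will be used to generate the comparison group from the clinical records". It names no matching variables, ratio, calliper or balance measure.

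On comparing the groups' characteristics, the same paragraph says: "Patient characteristics will be compared using the chi-square test", or Fisher's exact test, where the variable is categorical, and "For continuous variable data, the Wilcoxon test or Student's t test will be employed". The general criterion is: "A p-value less than 0.05 will be required to establish significance". The paragraph also provides for means with SDs or medians with ranges, and for counts with percentages. Outcomes are analysed by Kaplan-Meier, log-rank and a Cox model for which no covariates are named. Version A has the same wording; the amendment did not change it.

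**The concern.** Participants and matched registry patients are the only two groups in the study, so these tests are the plan's only between-group comparison of characteristics. Whether a match has worked is a question about the patients in hand: how far apart are the two groups on each prognostic variable? A p value mixes that distance with the sample size. With 20 participants it can stay above 0.05 while the groups differ materially. Discarding unmatched records also shrinks the sample, so p values can rise even when balance has not improved.

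The efficacy estimate depends on the match. If a prognostic difference goes unrecognised and the Cox model is unadjusted, the difference is carried into the hazard ratio and reads as a drug effect, or hides one.

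**Working it through.** The documents give no power, effect size or balance figure, so there is nothing to reproduce. The check asks what the planned tests can detect and what they let through.

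**Inputs from the documents:** 20 participants; p<0.05; 20 days of follow-up; age-specific mortality in Section 1.3.

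**Assumptions:** two-sided testing (sidedness is not stated); 1:1 matching, with a range to 1:5 (the ratio is not stated); a covariate effect, median recovery time and distribution as given in step 4.

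**1. Smallest observed difference that a t test calls significant.** With n1 = 20 participants and n2 controls, the limit in SD units is t(0.975, n1+n2−2) × √(1/n1 + 1/n2).

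| Ratio | t × √ | Limit (SD) |
|---|---|---|
| 1:1 | 2.024 × 0.316 | 0.64 |
| 1:2 | 2.002 × 0.274 | 0.55 |
| 1:3 | 1.991 × 0.258 | 0.51 |
| 1:5 | 1.980 × 0.245 | 0.49 |

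Anything smaller gives p>0.05. More controls help little, because the 20 participants set the precision.

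**2. Chance of flagging a true imbalance** (noncentral t, 20 v 20): 12% at 0.25 SD, 23% at 0.4 SD, 34% at 0.5 SD, 69% at 0.8 SD. At 1:5 the figure for 0.5 SD is 53%. For 80% power to flag 0.25 SD, the test would need about 252 per group.

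**3. A binary characteristic, 6/20 v 12/20 (30% v 60%).** Fisher's exact p = 0.11. The expected counts are 9 and 11, so chi-square is also usable: uncorrected, χ² = 40 × (6×8 − 14×12)² / (20 × 20 × 18 × 22) = 3.64, p = 0.057. Both are non-significant, the second narrowly. Against 6/20, uncorrected chi-square first reaches significance at 13/20 and Fisher at 14/20.

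**4. Effect on the recovery hazard ratio with an inert drug.** Assume one normally distributed covariate that multiplies the recovery rate by 0.6 per SD and is less favourable in the controls. Conditional on the covariate, the bias is 0.6^−d: 0.6^−0.4 = 1.23 and 0.6^−0.64 = 1.39. The planned model names no covariates, so the unadjusted ratio is the relevant one, and it is closer to 1. Simulation with a 9-day median and censoring at day 20 gives about 1.19 at 0.4 SD and 1.33 at 0.64 SD. For a weaker covariate, at 1.2 per SD, the conditional values are only 1.2^0.4 = 1.08 and 1.2^0.64 = 1.12. If the imbalance runs the other way, so does the bias.

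**5. Illustration from the protocol's own age figures.** Section 1.3 gives mortality of 1.3% to 3.6% at ages 40 to 69 and 8% above 70. Suppose 6/20 participants and 12/20 controls are above 70 and the rest are aged 40 to 69. With the younger rate at 1.3%, expected mortality is 0.3×8 + 0.7×1.3 = 3.3% v 0.6×8 + 0.4×1.3 = 5.3%, a ratio of 0.62. With the younger rate at 3.6% it is 4.9% v 6.2%, a ratio of 0.79. These are general rates, not rates for hospitalized patients, and show relative prognosis only.

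**6. False significance.** In simulations with an inert drug, a true imbalance of 0.5 to 0.6 SD and covariate effects of 1.5 to 3 per SD, the two-sided log-rank test rejected in about 6% to 9% of the samples whose balance test was non-significant, against a nominal 5%.

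**The case against.** The strongest reply is that the plan never uses these tests as a gate. A reader might infer that the match is accepted when nothing is significant, but no sentence says so. The sentence on tests does not mention matching, and the p<0.05 sentence is a general statement about significance. This stands: the plan cannot be charged with an acceptance rule that it does not state.

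Nor are the tests the only information. Means, SDs and percentages will be shown, and a careful reader would notice 30% v 60%. That also stands, but the plan says nothing about what follows when an imbalance is seen.

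The size depends on assumptions. The number of controls is not given, and 0.64 is the top of the range shown. The 0.6 per SD has no source in the documents. The conclusion survives the first point, since the limit is still 0.49 at 1:5. The second makes the hazard ratios illustrations only.

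Finally, a strict limit on standardized differences may be unattainable. Under simple randomization at 20 v 20, one covariate falls below 0.25 about 57% of the time, and five independent covariates all do so about 6% of the time (0.566^5 = 0.058). Matching can do better on measured variables, but a hard gate on every variable could leave no acceptable match. This stands and shapes the remedy.

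**Conclusion.** The point holds as a weakness in the chosen method. Significance testing is the plan's only between-group comparison of characteristics, and no balance measure or response to imbalance is attached to the match. The detection limits (0.64 SD at 1:1, 0.49 SD at 1:5) rest only on 20 participants, a two-sided 0.05 t test and the ratio shown. The hazard ratio of about 1.19 to 1.33 also rests on the assumed 0.6 per SD, 9-day median and day-20 censoring, and is smaller for weaker covariates.

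A reader might go further and infer that the plan will produce a falsely significant drug effect. The calculations do not support that as the main harm: rejection rises only modestly on average, although it is more likely when the observed imbalance lies close to the limit. The main harm is a biased estimate reported without a measure that would reveal it. The change should be made; it is cheap, and the efficacy comparison depends on the match.

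**What to change.** In the Statistical Analysis Plan of Version B:

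- Assess the match by standardized mean differences before and after matching for every matching variable, instead of relying on p values.
- State a limit in advance, for example 0.25, as a trigger rather than a hard acceptance gate.
- If it is exceeded, re-specify the propensity model or calliper without sight of outcomes.
- If imbalance remains, adjust the Cox model for a small pre-specified set of key prognostic variables (for example age and baseline oxygen status), or for the propensity score.
- Report the residual imbalance openly beside the hazard ratio.

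The cost is some SAP wording, one extra table and possibly a repeat of the matching. With 1:1 matching there are at most 40 recoveries (20 + 20), so few covariates can be afforded, and some imbalance may have to be shown rather than removed.
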